4.1 Description of Study Design

This is a single-arm, open-label feasibility study. 30 subjects will be screened and consented for a maximum enrollment of 15 participants. All participants will undergo a novel neurofeedback intervention, targeting down-regulation of deep limbic structures, specifically the amygdalae. Participants will complete 15 neurofeedback sessions delivered twice weekly over 8 consecutive weeks. The intervention will be delivered via the PRISM platform. Parts of this study will be conducted in clinic and parts are conducted remotely. Clinician assessments and self-questionnaires will be done remotely. The Prism intervention will be conducted in the clinic.

4.2 Study Endpoints

4.2.1 Primary Study Endpoints

Demonstrate the NYU team can successfully recruit, enroll, and complete the protocol as proof of concept and collect high-quality analyzable data.

4.2.2 Secondary Study Endpoints

30% meaningful improvement on primary outcome measures (AISRS and ASRS/BRIEF-A) demonstrated by effect size of change scores.

5.0 Study Enrollment and Withdrawal

5.1 Inclusion Criteria

In order to be eligible to participate in this study, an individual must meet all of the following criteria:

#	Criteria	Method of
		Assessment
1	Adults ages 18-60 years, inclusive at the time of consent	ID
2	Able to provide signed informed consent	ICF Teach-
		Back
3	Any gender	Self-Report
4	Subjects with a current primary DSM-5 diagnosis of ADHD	Clinical
	(including predominantly inattentive	Interview
	presentation, hyperactive presentation, or combined	
	presentations) as confirmed by the ACDS	
	Version 1.2.	
5	Subjects who are not receiving any pharmacological treatment for	
	ADHD must have an AISRS score of ≥ 28 at screening. Subjects	
	who are receiving pharmacological treatment for ADHD at	
	screening must have a minimum AISRS score of ≥ 22 at screening	
6	Not requiring treatment for any comorbid psychiatric condition for	
	at least 2 months	
7	Normal or corrected-to-normal vision	Self-Report
8	Normal or corrected-to-normal hearing	

No intention of changing medication or psychotherapy for the 9 duration of the study at the time of recruitment

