2.3 Rationale

Approximately 4.4% of the U.S. population aged 18-44 years meet criteria for adult ADHD based on a replication of the National Comorbidity Study (Kessler RC et al., 2006). ADHD is a neuropsychiatric disorder characterized by problems with sustaining attention, organization, planning, procrastination, day-dreaming, restlessness, impulsivity and hyperactivity. Psychostimulant medications are the mainstay for treating ADHD as they have shown to be highly effective in symptom reduction. Non stimulant medication is highly recommended as a first-line of treatment for ADHD as well for those who cannot tolerate the side effects some stimulant medications may carry. Psychological treatments have been found to be moderately effective for treating ADHD. Compared to pharmacotherapy, the effect sizes are smaller but the promise for treating ADHD with nonpharmacological interventions is there (Cortese et al., 2015; Sonuga-Barke et al., 2013). Cognitive Behavioral Therapy (CBT) has been shown to be efficacious in improving symptoms of ADHD in various clinical and randomized controlled trials. Especially when combined with a pharmacotherapy, CBT has shown positive results in controlling symptoms of ADHD (Ramsay & Rostain 2014). However, the evidence basis for psychosocial therapies as a stand-alone treatment for ADHD still require more research. Thus, there is a clear need to expand upon the nonpharmacological evidence base and explore alternative and adjunctive therapies to improve outcomes for patients with ADHD. This pilot study will demonstrate that the NYU team can successfully recruit, enroll, and complete the protocol as proof of concept and collect high-quality analyzable data in preparation for later clinical trials.

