5.2 Exclusion Criteria

An individual who meets any of the following criteria will be excluded from participation in this study:

#	Criteria	Method of
		Assessment
1	Concurrent substance abuse and/or history of substance use	Clinical
	within 6 months	Interview
2	Use of any prescribed benzodiazepine	
3	Lifetime bipolar disorder, psychotic disorder, autism,	
	intellectual disability. Comorbid mood and anxiety disorders	
	determined by the MINI will be permitted if they are not the	
	primary focus of clinical attention	
4	Active suicidality within past year, or history of suicide attempt	
	in past 2 years	
5	Any history of severe past drug dependence determined by the	
	MINI (i.e., a focus of clinical attention or a cause of substantial	
	social or occupational difficulty)	
6	Any unstable medical or neurological condition	
7	Any history of brain surgery, of penetrating, neurovascular,	
	infectious, or other major brain injury, of epilepsy, or of other	
	major neurological abnormality (including a history of	
	traumatic brain injury [TBI] with loss of consciousness for more	
	than 24 hours or posttraumatic amnesia for more than 7 days)	
8	Any psychotropic medication	
9	Recent initiation (within the past 3 months) of cognitive-	
	behavioral therapy or any evidence-based PTSD psychotherapy	
	(Cognitive Processing Therapy [CPT], Prolonged Exposure	
	[PE], Eye Movement Desensitization and Reprocessing	
	[EMDR]); continuation of established maintenance supportive	
	therapy will be permitted	~ 14 F
10	Significant hearing loss or severe sensory impairment	Self-Report

11	Enrollment in another research study testing an experimental,	
	clinical, or behavioral intervention intended to affect symptoms	
	initiated within the last 2 months, or intended enrollment	
	within the next 2.5 months	

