7.3 Concomitant Medications, Treatments, and Procedures

All concomitant medications taken during study participation will be recorded on the case report forms (CRFs). Medications to be reported in the CRF are concomitant prescription medications, over-the-counter medications and non-prescription medications. For this protocol, a prescription medication is defined as a medication that can be prescribed only by a properly authorized/licensed clinician.

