10.1 Statistical and Analytical Plans (SAP)

This pilot study is not formally powered to assess effect statistically. We will: demonstrate the NYU team can successfully recruit, enroll, and complete the protocol as proof of concept and collect high-quality analyzable data; and assess clinically meaningful improvement on primary outcome measures (AISRS and ASRS/BRIEF-A) as demonstrated by effect size of change.

As this is a pilot study and the full estimation of the potential magnitude of the effect is not known, we are planning an interim analysis after completion of approximately 10 patients with treatment data. This interim analysis examine the magnitude of clinical effects on clinical measures of AISRS expanded AISRS subsets (clinician symptom measure), ASRS (self-report symptom measure), BRIEF (self-report measure of executive function) and CGI (measure of impairment) via examination for means, SDs and magnitude of effect. Safety data will also be examined.

ADHD Rationale

In this study, approximately 30 subjects will be phone prescreened, which will give us at least 30 participants coming in for screening and consenting for participation. Up to 30 patients will be enrolled/consented to be sure that 15 evaluable/assigned

CONFIDENTIAL

patients reach the end of PRISM Intervention. We expect some of the subjects to screen fail either during the telephone phone screen or during the hybrid remote visit. Screen failures can occur during the MINI (psychiatric interview), ACDS (ADHD diagnosis interview) or upon discretion of the principal investigator. Subjects are also given the opportunity to continuously decide participation throughout the study. Subjects can opt out of the study at any time.

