10.2 Sample Size

We will consent approximately 30 participants to meet our goal of 15 completers.

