10.3 Measures to Minimize Bias

10.3.1 Enrollment/Randomization/Masking Procedures

Blinding, randomization, and masking are considered unnecessary for this pilot study. All subjects will undergo the same procedures.

11 Source Documents and Access to Source Data/Documents

Source data is all information, original records of clinical findings, observations, or other activities in a clinical trial necessary for the reconstruction and evaluation of the trial. Source data are contained in source documents. Examples of these original documents, and data records include: hospital records, clinical and office charts, laboratory notes, memoranda, subjects' diaries or evaluation checklists, pharmacy dispensing records, recorded data from automated instruments, copies or transcriptions certified after verification as being accurate and complete, microfiches, photographic negatives, microfilm or magnetic media, x-rays, subject files, and records kept at the pharmacy, at the laboratories, and at medico-technical departments involved in the clinical trial. It is acceptable to use CRFs as source documents. If this is the case, it should be stated in this section what data will be collected on CRFs and what data will be collected from other sources.

The study case report form (CRF) is the primary data collection instrument for the study. All data requested on the CRF must be recorded. All missing data must be explained. If a space on the CRF is left blank because the procedure was not done or the question was not asked, write "N/D". If the item is not applicable to the individual case, write "N/A". All entries should be printed legibly in black ink. If any entry error has been made, to correct such an error, draw a single straight line through the incorrect entry and enter the correct data above it. All such changes must be initialed and dated. DO NOT ERASE OR WHITE OUT ERRORS. For clarification of illegible or uncertain entries, print the clarification above the item, then initial and date it.

Access to study records will be limited to IRB-approved members of the study team. The investigator will permit study-related monitoring, audits, and inspections by the IRB/EC, the sponsor, government regulatory bodies, and University compliance and

CONFIDENTIAL

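### No settled period on or off ADHD medication is required at entry, and the analysis ignores medication changes, so drug effects can enter the single-arm change scores in either direction

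*Combined protocol and SAP*

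**What the plan says.** **Entry.** Inclusion 5 (section 5.1) admits people on ADHD drug treatment with a screening AISRS of at least 22, and people on none with at least 28. Neither branch sets a minimum time in that state. Inclusion 9 requires "No intention of changing medication or psychotherapy" over the study, judged at recruitment.

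**Windows that do exist.** Exclusion 9 (section 5.2) begins "Recent initiation (within the past 3 months) of cognitive" and goes on to cover behavioral therapy of that kind and named PTSD psychotherapies. Inclusion 6 uses 2 months for treatment of comorbid conditions. Exclusion 11 uses 2 months for other research interventions, counted from their initiation.

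**Exclusion 8** bars psychotropic medication without any time window. Read literally, it conflicts with the medicated branch of Inclusion 5.

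**Design and analysis.** Section 4.1 states "This is a single-arm, open-label feasibility study", and section 10.3.1 adds "Blinding, randomization, and masking are considered unnecessary for this pilot study". Section 7.3 has concomitant medications recorded on the case report forms. Section 10.1 plans an effect size of change, and an interim look at about 10 patients using means, SDs and magnitude of effect. It gives no rule for a medication start, stop or dose change.

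**The concern.** The protocol already treats a recently started therapy as a threat to interpreting change, since it sets a window for CBT and PTSD therapies. It sets none for ADHD medication. Yet section 2.3 says "Psychostimulant medications are the mainstay for treating ADHD as they have shown to be highly effective in symptom reduction" and describes psychological treatments as having smaller effects than pharmacotherapy. The weaker competing explanation is guarded against and the stronger one is left open.

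With no control arm, change over time is the whole clinical result, and nothing in the design separates a drug effect from a neurofeedback effect. At stake are the secondary endpoint (4.2.2), the interim estimate (10.1) and Objective 3 (3.1). Section 2.3 describes the study as preparation for later trials, so these figures may be read with those in mind.

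**Working it through.** **1. The plan's own figure.** Section 10.2: "We will consent approximately 30 participants to meet our goal of 15 completers". Section 10.1: "This pilot study is not formally powered to assess effect statistically". No alpha, power, effect size, SD or drug effect is given. The only arithmetic available is 15 / (1 − 0.5) = 30, and the 50% loss is implied by the two numbers rather than stated. So 15 cannot be derived independently, and the documents offer no scale for a bias.

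**2. Exposure window.** Baseline is Week 1 (7.2.2), the last session Week 9 (7.2.4) and the final visit Week 11 (7.2.5).
- Baseline to last session: 9 − 1 = 8 weeks.
- Baseline to final visit: 11 − 1 = 10 weeks.
- Screening to baseline: 7 ± 5 days, so 2 to 12 days.

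**3. Who can enter, under each reading of the medication criteria.**

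| Reading | Recent starter | Recent stopper |
|---|---|---|
| Inclusion 5 governs | Can enter at AISRS ≥ 22 | Can enter at AISRS ≥ 28 |
| Exclusion 8 governs | Barred, for psychotropic drugs | Can enter at AISRS ≥ 28; no look-back |

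The recruitment sources make this plausible. Section 5.4 expects most participants from clinical referrals and also lists an earlier ADHD drug trial. Because Exclusion 11 counts from initiation, someone who joined such a trial more than 2 months ago and has just come off its drug passes.

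**4. Illustration of size. Every value of k, D and SD here is assumed.** Let k of n = 15 completers each have D AISRS points of drug effect still to come after baseline, and let p = k/15.
- Shift in mean change = k × D / 15.
- Spurious d = shift / √(SD² + p(1 − p)D²), with SD = 8.

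| k | D | Shift (points) | d |
|---|---|---|---|
| 1 | 5 | 5/15 = 0.33 | 0.33 / √(64 + 1.56) = 0.04 |
| 3 | 10 | 30/15 = 2.0 | 2.0 / √(64 + 16) = 0.22 |
| 4 | 15 | 60/15 = 4.0 | 4.0 / √(64 + 44) = 0.38 |

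For the middle row, an SD of 6 gives 2.0 / √(36 + 16) = 0.28 and an SD of 10 gives 2.0 / √(100 + 16) = 0.19. The table describes continued improvement after a recent start. If people who recently stopped worsen after baseline, the sign reverses.

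**5. Weight of one person.** Each participant is 1/15 = 6.7 percentage points of a 30%-improvement rate at the end and 1/10 = 10 points at the interim look. A 30% improvement from the entry minima is 0.3 × 22 = 6.6 or 0.3 × 28 = 8.4 points, so one drug change of that order could by itself carry a person across the threshold.

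**The case against.** **Safeguards exist.** Section 7.4 makes the exclusion criteria the list of prohibited treatments, and section 5.7.1 lets the investigator terminate someone who newly meets one. The phone pre-screen takes medication history, a person with a planned titration arguably fails Inclusion 9, and section 10.1 allows screen failure at the principal investigator's discretion. These narrow the gap but do not close it. Termination is optional, discretion is not a criterion, and a person whose change is already made has no intention left to declare. Section 7.2.6 also asks anyone terminated early for a final visit, and the plan does not say whether ratings after a drug change count.

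**The mechanism is not demonstrated.** Section 2.1 describes stimulant doses as acting for a couple of hours to all day. Nothing in the documents shows a large effect still unfolding after baseline, and a drug effect complete by baseline adds no bias. This stands. It limits the point to changes still under way, whose frequency is unknown.

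**Exclusion 8, if it governs, closes the starter route** for psychotropic drugs. That also stands. The table in step 4 would then not apply, and only recent stoppers would remain, with an uncertain direction.

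**The study is an unpowered pilot, and uncontrolled change is not causal evidence anyway.** True, and it lowers the severity. It does not justify leaving an avoidable extra source of drift in the estimate.

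**Stronger readings to avoid.** A reader might infer that the primary endpoint is compromised; section 4.2.1 concerns recruitment, completion and data quality, not symptom change. A reader might infer that the gap flatters PRISM; it can work either way. A reader might infer that psychotherapy in general must be settled before entry; Exclusion 9 covers only starting CBT or listed PTSD therapies.

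**Conclusion.** The point holds in limited form. No entry criterion requires a settled period since starting, stopping or changing ADHD medication, this is so under either reading of Inclusion 5 and Exclusion 8, and section 10.1 makes no use of the medications recorded. Drug-related change still under way after baseline would be counted in the secondary, interim and Objective 3 estimates over 8 weeks (to Week 9) or 10 weeks (to Week 11), in either direction.

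The magnitude is not known. The range of d from 0.04 to 0.38 rests on an assumed 1 to 4 affected people, 5 to 15 points each and an SD of 8, and it describes recent starters only. Severity is low to moderate.

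**What to change.** 1. **Eligibility.** Reconcile Inclusion 5 with Exclusion 8. Then add to section 5.1 that ADHD medication status has been unchanged for a fixed period before screening. The sponsor should set the length; the protocol already uses 2- and 3-month windows elsewhere. This line deals with changes made before entry.
2. **Data.** Record start, stop and dose-change dates on the existing concomitant-medication form. Sections 7.1 and 7.3 say medications are recorded but do not mention dates.
3. **Analysis.** In section 10.1, report the change estimate from all ratings and, beside it, the estimate using only ratings made before any change in ADHD or other psychotropic medication. This deals with changes during the study. Making the restricted estimate the main one would be debatable at n = 15, because it loses late ratings and the plan has no method for handling them; showing both avoids that choice.

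**Cost.** One reconciled pair of criteria, one eligibility line, date fields on an existing form and one analysis sentence. A few candidates would wait or be screened out, and the restricted estimate would rest on fewer late ratings. No participant's treatment is altered.

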5.2 Exclusion Criteria

An individual who meets any of the following criteria will be excluded from participation in this study:

#	Criteria	Method of
		Assessment
1	Concurrent substance abuse and/or history of substance use	Clinical
	within 6 months	Interview
2	Use of any prescribed benzodiazepine	
3	Lifetime bipolar disorder, psychotic disorder, autism,	
	intellectual disability. Comorbid mood and anxiety disorders	
	determined by the MINI will be permitted if they are not the	
	primary focus of clinical attention	
4	Active suicidality within past year, or history of suicide attempt	
	in past 2 years	
5	Any history of severe past drug dependence determined by the	
	MINI (i.e., a focus of clinical attention or a cause of substantial	
	social or occupational difficulty)	
6	Any unstable medical or neurological condition	
7	Any history of brain surgery, of penetrating, neurovascular,	
	infectious, or other major brain injury, of epilepsy, or of other	
	major neurological abnormality (including a history of	
	traumatic brain injury [TBI] with loss of consciousness for more	
	than 24 hours or posttraumatic amnesia for more than 7 days)	
8	Any psychotropic medication	
9	Recent initiation (within the past 3 months) of cognitive-	
	behavioral therapy or any evidence-based PTSD psychotherapy	
	(Cognitive Processing Therapy [CPT], Prolonged Exposure	
	[PE], Eye Movement Desensitization and Reprocessing	
	[EMDR]); continuation of established maintenance supportive	
	therapy will be permitted	~ 14 F
10	Significant hearing loss or severe sensory impairment	Self-Report

11	Enrollment in another research study testing an experimental,	
	clinical, or behavioral intervention intended to affect symptoms	
	initiated within the last 2 months, or intended enrollment	
	within the next 2.5 months	

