3.1 Primary Objectives

The primary objectives of this pilot study are as follows:

- 1. To train the NYU team on EFP-EEG-NF technology and provide them with hands-on experience.
- 2. To assess participants' ability to learn the feedback paradigm (i.e. control the EFP-EEG-NF signal; time to achieve learning; and assess learning curves).
- 3. To explore preliminary results assessing emotional dysregulation measured on subsets of AISRS and BRIEF-A.

4 Study Design and Endpoints

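### Exclusion 9 applies its three-month settled period only to CBT and PTSD psychotherapies, so newly started coaching, non-CBT skills training or computer-based training for ADHD can enter a single-arm change score

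*Combined protocol and SAP*

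**What the plan says.** **Section 5.2, exclusion 9.** The criterion begins "Recent initiation (within the past 3 months) of cognitive" and continues "behavioral therapy or any evidence-based PTSD psychotherapy", naming three PTSD therapies (CPT, PE and EMDR). It ends with an allowance: "EMDR]); continuation of established maintenance supportive" therapy is permitted.

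**Section 5.1, inclusion 9.** "No intention of changing medication or psychotherapy" during the study, judged at recruitment.

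**Section 3.1, third objective.** "To explore preliminary results assessing emotional dysregulation measured on subsets of AISRS and BRIEF-A".

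**Section 4.2.2.** The secondary endpoint is a 30% improvement on AISRS and ASRS/BRIEF-A, expressed as an effect size of change scores. Section 10.1 adds an interim look at effect magnitude after about 10 treated patients.

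**Section 7.3.** Concomitant recording is specified for medications: prescription, over-the-counter and non-prescription. The schedule in Section 7.1 has a row for prior and concomitant medications and none for psychosocial treatment.

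**The concern.** Criterion 9 accepts a principle: a recently started psychological treatment may still be producing change, so a settled period is needed before change is measured. The plan chose three months. Apart from CBT, however, the therapies it names are for PTSD. Treatments aimed at what this trial measures are not named. Examples are ADHD coaching, non-CBT skills training or emotion-regulation programs, computer-based attention training, and conventional neurofeedback obtained outside a research study.

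Section 2.3 itself describes psychological treatments as moderately effective in ADHD, so the plan gives its own reason to expect some gain from them. In a single-arm, open-label study no comparison group carries the same concurrent gains. They would be counted in the AISRS, ASRS and BRIEF-A change that the plan reports as the clinical signal, and in the interim look, where fewer patients give each recent starter more weight.

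**Working it through.** **1. Does any other provision close the gap?** Take a person who began ADHD coaching two weeks before screening and plans to continue.

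- Exclusion 9: coaching is neither CBT nor a PTSD psychotherapy, so the person is not excluded.
- Inclusion 9 ("No intention of changing medication or psychotherapy for the" study period): no change is intended, so it is met. It sets no minimum time on current treatment.
- Inclusion 6 ("Not requiring treatment for any comorbid psychiatric condition for" at least two months): this concerns comorbid conditions, not psychosocial treatment of ADHD.
- Exclusion 11 ("Enrollment in another research study testing an experimental" or other intervention): this covers research studies, not community treatment.
- Section 7.4: refers back to the exclusion criteria and adds nothing.
- Section 10.1: mentions screen failure at the principal investigator's discretion, which is not a stated rule, and plans no analysis that accounts for concurrent psychosocial treatment.

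Nothing in the text keeps this person out. Nothing explicitly requires the coaching to be recorded either, although the psychiatric history might pick it up.

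**2. How large could the effect be?** The plan gives no figure to reproduce: no SD, no expected change, and no rate of recent starters.

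From the documents: 15 completers (Section 10.2); about 10 patients at the interim look (Section 10.1); AISRS entry minimum of 28 without ADHD medication and 22 with it (Section 5.1).

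Assumed: k = 1 to 3 recent starters among completers; extra gain g = 5 to 10 AISRS points, all after baseline; SD of change 8; underlying mean change 8 points.

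*Shift in mean change* = k × g / n.

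| | n = 15 | n = 10 (interim) |
|---|---|---|
| k = 1, g = 5 | 5/15 = 0.33 | 5/10 = 0.5 |
| k = 3, g = 10 | 30/15 = 2.0 | 30/10 = 3.0 |

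For scale, 30% of the entry minimum is 0.30 × 28 = 8.4 or 0.30 × 22 = 6.6 points. The worst case at n = 15 is 2.0/8.4 = 24% or 2.0/6.6 = 30% of that amount.

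*Standardized effect, worst case.* Mixing starters and non-starters also widens the SD. The share of starters is 3/15 = 0.2.

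- Added variance: 0.2 × 0.8 × 10² = 16.
- SD: √(64 + 16) = 8.94.
- Effect without starters: 8/8 = 1.00. With starters: (8 + 2)/8.94 = 1.12. Increase: about 0.12.

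*Lowest case* (k = 1, g = 5).

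- Added variance: (1/15) × (14/15) × 25 = 1.56.
- SD: √65.56 = 8.10.
- Effect: 8.33/8.10 = 1.03. Increase: about 0.03.

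The increase depends on the assumed underlying change. With none at all, the worst case would be 2.0/8.94 = 0.22.

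**3. How likely is at least one such entrant?** If each completer independently has a 10% chance of being a recent starter (assumed), the probability is 1 − 0.9¹⁵ = 0.79. At 5% it is 0.54 and at 20% it is 0.96.

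**The case against.** **Much of the ground is already covered.** CBT is the psychosocial ADHD treatment that Section 2.3 singles out as efficacious, and criterion 9 names it first. A skills or emotion-regulation program delivered as CBT is already excluded. The supportive-therapy clause speaks of established treatment, which points against new starters without barring them. A short course due to end within the study arguably fails inclusion 9. All of this stands, and it narrows the gap to coaching, non-CBT programs, and computer-based or conventional neurofeedback training.

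**The list is not simply wrong.** A reader might infer that the PTSD therapies are aimed at the wrong disorder and should be replaced. The documents do not support that. Section 5.4 recruits through veteran and military sources, and exclusion 3 permits comorbid mood and anxiety disorders. A replacement limited to ADHD-related targets would also lift criterion 9's bar on recent CBT for depression, anxiety or sleep, although PHQ-9, HAM-A and PSQI are measured before and after the intervention.

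**The size is small against the noise.** With an SD of 8 and n = 15, the standard error is 8/√15 = 2.07, and the 95% half-width is about 4.4 points (t = 2.145 on 14 degrees of freedom). Even the 2.0-point worst case is within one standard error. Gain made before the Week 1 baseline does not count in change from that baseline. Dividing 2.0 by a fixed SD of 8 suggests 0.25, but that ignores the wider SD of a mixed sample. These points stand. The shift is nevertheless a bias in one direction, whereas the standard error describes random scatter.

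**The stakes are limited.** The primary endpoint is feasibility, the study is not formally powered, and without a control arm change cannot be attributed to PRISM in any case. That is correct. It does not explain why a confounder that the plan already chose to limit should be limited for some therapies and not for those closest to the outcomes.

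**Conclusion.** The gap is real but modest. The settled period does not reach newly started non-CBT, non-drug treatments aimed at ADHD symptoms, executive function or emotion regulation, and no other provision reaches them. Any gain from such treatment would be indistinguishable from PRISM in the secondary change scores and the interim look. It is not certain that such people will enroll or that they will gain.

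The illustrated size is 0.3 to 2.0 AISRS points on the mean, and about 0.03 to 0.12 on the standardized effect. Both rest on assumed values of k and g; the second also rests on an assumed SD of 8 and underlying change of 8 points. None of these is in the documents.

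A reader might go further and infer that the feasibility result is compromised. The documents do not support this: recruitment, completion and data quality do not depend on concurrent treatment, and the primary endpoint is touched only by the few extra screen failures that the change would cause. This is a cheap improvement worth making, not a flaw that undermines the study.

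**What to change.** Keep the CBT and PTSD list in criterion 9 and keep the supportive-therapy allowance. Add a clause covering recent initiation, within the window the criterion already uses, of any psychotherapy, coaching, skills training or computer-based treatment aimed at ADHD symptoms, executive function or emotion regulation.

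In Section 7.3 and the schedule, record such treatment at screening and during the study, alongside concomitant medications, so that the change scores can be read with this information to hand.

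The cost is one added clause, a question in the existing clinical interview, one more item on the case report form, and a few more screen failures. The screen failures fall on recruitment, which is part of the primary endpoint. Because Section 7.4 defines prohibited treatments by pointing to the exclusion criteria, the authors should also state whether the added clause is meant to apply only at entry.
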